10.3.1. Definition of AE

AE Definition

• An AE is any untoward medical occurrence in a patient or clinical study participant, temporally associated with the use of study intervention, whether or not considered related to the study intervention.• NOTE: An AE can therefore be any unfavorable and unintended sign (including an abnormal laboratory finding), symptom, or disease (new or exacerbated) temporally associated with the use of study intervention.

Events Meeting the AE Definition

• Any abnormal laboratory test results (hematology, clinical chemistry, or urinalysis) or other safety assessments (eg, ECG, radiological scans, vital sign measurements), including those that worsen from baseline, considered clinically significant in the medical and scientific judgment of the investigator Any abnormal laboratory test results that meet any of the conditions below must be recorded as an AE:
• Is associated with accompanying symptoms.• Requires additional diagnostic testing or medical/surgical intervention.• Leads to a change in study dosing (outside of any protocol-specified dose adjustments) or discontinuation from the study, significant additional concomitant drug treatment, or other therapy.• Exacerbation of a chronic or intermittent preexisting condition including either an increase in frequency and/or intensity of the condition.• New conditions detected or diagnosed after study intervention administration even though it may have been present before the start of the study.• Signs, symptoms, or the clinical sequelae of a suspected drug-drug interaction.• Signs, symptoms, or the clinical sequelae of a suspected overdose of either study intervention or a concomitant medication. Overdose per se will not be reported as an AE/SAE unless it is an intentional overdose taken with possible suicidal/self-harming intent. Such overdoses should be reported regardless of sequelae.

Events NOT Meeting the AE Definition

- Any clinically significant abnormal laboratory findings or other abnormal safety assessments which are associated with the underlying disease, unless judged by the investigator to be more severe than expected for the participant's condition.
- The disease/disorder being studied or expected progression, signs, or symptoms of the disease/disorder being studied, unless more severe than expected for the participant's condition.
- Medical or surgical procedure (eg, endoscopy, appendectomy): the condition that leads to the procedure is the AE.
- Situations in which an untoward medical occurrence did not occur (social and/or convenience admission to a hospital).
- Anticipated day-to-day fluctuations of preexisting disease(s) or condition(s) present or detected at the start of the study that do not worsen.

10.3.2. Definition of SAE

If an event is not an AE per definition above, then it cannot be an SAE even if serious conditions are met (eg, hospitalization for signs/symptoms of the disease under study, death due to progression of disease).

An SAE is defined as any untoward medical occurrence that, at any dose:

a. Results in death

b. Is life-threatening

The term “life-threatening” in the definition of “serious” refers to an event in which the participant was at risk of death at the time of the event. It does not refer to an event that hypothetically might have caused death if it were more severe.

c. Requires inpatient hospitalization or prolongation of existing hospitalization

In general, hospitalization signifies that the participant has been detained (usually involving at least an overnight stay) at the hospital or emergency ward for observation and/or treatment that would not have been appropriate in the physician's office or outpatient setting. Complications that occur during hospitalization are AEs. If a complication prolongs hospitalization or fulfills any other serious criteria, the event is serious. When in doubt as to whether “hospitalization” occurred or was necessary, the AE should be considered serious.

Hospitalization for elective treatment of a preexisting condition that did not worsen from

baseline is not considered an AE.

d. Results in persistent disability/incapacity
 
• The term disability means a substantial disruption of a person's ability to conduct normal life functions.• This definition is not intended to include experiences of relatively minor medical significance such as uncomplicated headache, nausea, vomiting, diarrhea, influenza, and accidental trauma (eg, sprained ankle) which may interfere with or prevent everyday life functions but do not constitute a substantial disruption.

e. Is a congenital anomaly/birth defect


f. Other situations:
 
• Medical or scientific judgment should be exercised in deciding whether SAE reporting is appropriate in other situations such as important medical events that may not be immediately life-threatening or result in death or hospitalization but may jeopardize the participant or may require medical or surgical intervention to prevent one of the other outcomes listed in the above definition. These events should usually be considered serious.• Examples of such events include invasive or malignant cancers, intensive treatment in an emergency room or at home for allergic bronchospasm, blood dyscrasias or convulsions that do not result in hospitalization, or development of drug dependency or drug abuse.• Suspected transmission via a Pfizer product of an infectious agent, pathogenic or non-pathogenic, is considered serious. The event may be suspected from clinical symptoms or laboratory findings indicating an infection in a patient exposed to a Pfizer product. The terms "suspected transmission" and "transmission" are considered synonymous. These cases are considered unexpected and handled as serious expedited cases by pharmacovigilance personnel. Such cases are also considered for reporting as product defects, if appropriate.

10.3.3. Recording/Reporting and Follow-up of AEs and/or SAEs

AE and SAE Recording/Reporting		
The table below summarizes the requirements for recording adverse events on the CRF and for reporting serious adverse events on the CT SAE Report Form to Pfizer Safety. These requirements are delineated for 3 types of events: (1) SAEs; (2) nonserious adverse events (AEs); and (3) exposure to the study intervention under study during pregnancy or breastfeeding, and occupational exposure.		
It should be noted that the CT SAE Report Form for reporting of SAE information is not the same as the AE page of the CRF. When the same data are collected, the forms must be completed in a consistent manner. AEs should be recorded using concise medical terminology and the same AE term should be used on both the CRF and the CT SAE Report Form for reporting of SAE information.		
Safety Event	Recorded on the CRF	Reported on the CT SAE Report Form to Pfizer Safety Within 24 Hours of Awareness
SAE	All	All
Nonserious AE	All	None
Exposure to the study intervention under study during pregnancy or breastfeeding, and occupational exposure.	All AEs/SAEs associated with exposure during pregnancy or breastfeeding. Occupational exposure is not recorded.	All (and EDP supplemental form for EDP). Note: Include all SAEs associated with exposure during pregnancy or breastfeeding. Include all AEs/SAEs associated with occupational exposure.

- When an AE/SAE occurs, it is the responsibility of the investigator to review all documentation (eg, hospital progress notes, laboratory reports, and diagnostic reports) related to the event.
- The investigator will then record all relevant AE/SAE information in the CRF.
- It is **not** acceptable for the investigator to send photocopies of the participant's medical records to Pfizer Safety in lieu of completion of the CT SAE Report Form/AE/SAE CRF page.
- There may be instances when copies of medical records for certain cases are requested by Pfizer Safety. In this case, all participant identifiers, with the exception of the participant number, will be redacted on the copies of the medical records before submission to Pfizer Safety.

- The investigator will attempt to establish a diagnosis of the event based on signs, symptoms, and/or other clinical information. Whenever possible, the diagnosis (not the individual signs/symptoms) will be documented as the AE/SAE.

Assessment of Intensity

The investigator will make an assessment of intensity for each AE and SAE reported during the study and assign it to 1 of the following categories:

- Mild: An event that is easily tolerated by the participant, causing minimal discomfort and not interfering with everyday activities.
- Moderate: An event that causes sufficient discomfort and interferes with normal everyday activities.
- Severe: An event that prevents normal everyday activities. An AE that is assessed as severe should not be confused with an SAE. Severe is a category utilized for rating the intensity of an event; and both AEs and SAEs can be assessed as severe.

An event is defined as “serious” when it meets at least 1 of the predefined outcomes as described in the definition of an SAE, NOT when it is rated as severe.

AEs in the cardiac and blood/bone categories will be evaluated applying Common Terminology Criteria for Adverse Events (CTCAE) Version 5. For reporting purposes, CTCAE severity grades are to be interpreted as follows:

- Grade 1 events correlate to Mild.
- Grade 2 events correlate to Moderate.
- Grade 3 and higher events correlate to Severe.

Assessment of Causality

- The investigator is obligated to assess the relationship between study intervention and each occurrence of each AE/SAE.
- A “reasonable possibility” of a relationship conveys that there are facts, evidence, and/or arguments to suggest a causal relationship, rather than a relationship cannot be ruled out.
- The investigator will use clinical judgment to determine the relationship.
- Alternative causes, such as underlying disease(s), concomitant therapy, and other

risk factors, as well as the temporal relationship of the event to study intervention administration, will be considered and investigated.

- The investigator will also consult the IB and/or product information, for marketed products, in his/her assessment.
- For each AE/SAE, the investigator **must** document in the medical notes that he/she has reviewed the AE/SAE and has provided an assessment of causality.
- There may be situations in which an SAE has occurred and the investigator has minimal information to include in the initial report to the sponsor. However, **it is very important that the investigator always make an assessment of causality for every event before the initial transmission of the SAE data to the sponsor.**
- The investigator may change his/her opinion of causality in light of follow-up information and send an SAE follow-up report with the updated causality assessment.
- The causality assessment is one of the criteria used when determining regulatory reporting requirements.
- If the investigator does not know whether or not the study intervention caused the event, then the event will be handled as “related to study intervention” for reporting purposes, as defined by the sponsor. In addition, if the investigator determines that an SAE is associated with study procedures, the investigator must record this causal relationship in the source documents and CRF, and report such an assessment in the dedicated section of the CT SAE Report Form and in accordance with the SAE reporting requirements.

Follow-up of AEs and SAEs

- The investigator is obligated to perform or arrange for the conduct of supplemental measurements and/or evaluations as medically indicated or as requested by the sponsor to elucidate the nature and/or causality of the AE or SAE as fully as possible. This may include additional laboratory tests or investigations, histopathological examinations, or consultation with other healthcare providers.
- If a participant dies during participation in the study or during a recognized follow-up period, the investigator will provide Pfizer Safety with a copy of any postmortem findings including histopathology.
- New or updated information will be recorded in the originally completed CRF.
- The investigator will submit any updated SAE data to the sponsor within 24 hours

of receipt of the information.

10.3.4. Reporting of SAEs

SAE Reporting to Pfizer Safety via CT SAE Report Form

- Facsimile transmission of the CT SAE Report Form is the preferred method to transmit this information to Pfizer Safety.
- In circumstances when the facsimile is not working, notification by telephone is acceptable with a copy of the CT SAE Report Form sent by overnight mail or courier service.
- Initial notification via telephone does not replace the need for the investigator to complete and sign the CT SAE Report Form pages within the designated reporting time frames.

10.4. Appendix 4: Contraceptive Guidance

10.4.1. Male Participant Reproductive Inclusion Criteria

No contraception methods are required for male participants in this study, as the calculated safety margin is ≥ 100 -fold between the estimated maternal exposure due to seminal transfer and the NOAEL for serious manifestations of developmental toxicity in nonclinical studies.

10.4.2. Female Participant Reproductive Inclusion Criteria

A female participant is eligible to participate if she is not pregnant or breastfeeding, and at least 1 of the following conditions applies:

- Is not a WOCBP (see definitions below in [Section 10.4.3](#)).

OR

- For Part 1: Is a WOCBP and using a contraceptive method that is highly effective (with a failure rate of $<1\%$ per year), with low user dependency and not hormonally based, as described below during the intervention period and for at least 60 days ($7 \times$ terminal half-life) after the last dose of study intervention, which corresponds to the time needed to eliminate any reproductive safety risk of the study intervention(s). The investigator should evaluate the effectiveness of the contraceptive method in relationship to the first dose of study intervention.
- For Part 2: Is a WOCBP and using a contraceptive method that is highly effective (with a failure rate of $<1\%$ per year), with low user dependency (including hormonally based methods), or, is using contraceptive method that is highly effective (with a failure rate of $<1\%$ per year) that is not of low user dependency (including hormonally based methods) together with a barrier method as described below during the intervention period and for at least 60 days ($7 \times$ terminal half-life) after the last dose of study intervention, which corresponds to the time needed to eliminate any reproductive safety risk of the study intervention(s). The investigator should evaluate the effectiveness of the contraceptive method in relationship to the first dose of study intervention.

The investigator is responsible for review of medical history, menstrual history, and recent sexual activity to decrease the risk for inclusion of a woman with an early undetected pregnancy.

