Risks to study participants will be minimized by cautious dose escalation in an inpatient setting, with careful assessment and ongoing review of emerging safety data. Given that the overall potential risk of immunogenicity with PF-07242813 has been assessed to be moderate and that the cytokine release assay has suggested a low potential for cytokine release syndrome ([Section 2.2.1](#)), sentinel dosing will be implemented in all SAD cohorts (ie, cohorts where the dose being tested is the highest administered dose in the study to date). Sentinel dosing will involve administration of PF-07242813 or placebo to the first 2 participants randomized as 1: 1 in each SAD cohort, with observation for at least 24 hours to establish adequate safety and tolerability before dosing the remaining participants in the cohort.

Together, the implementation of sentinel dosing in SAD cohorts and the dose escalation rules ([Section 6.6.1](#)) are expected to minimize the risk to study participants while providing key safety and tolerability information. As is standard for FIH studies, dose administration will be conducted in the fasting state in order to facilitate management of any adverse events that may occur shortly after dosing.

CCI

associated safety concern at the last scheduled visits eg, Day 99 visit (~70 days after 3rd dose)
CCI [REDACTED]

[REDACTED]

Staining of neuroendocrine cells with PF-07242813 in the human anterior pituitary was observed in a tissue cross reactivity study that was not observed in the homologous cynomolgus monkey tissues ([Section 2.2.1](#)). The overall risk of pituitary toxicity in humans is considered low; however selected anterior pituitary hormones and hormones regulated by them will be monitored in SAD/MAD cohorts as a screen for potential adverse effects on the pituitary gland.

Currently, the final scheduled out-patient visits in SAD and MAD cohorts (except Cohorts 1-3 in SAD) are planned to be approximately 70 days after last dose, which is >4 times of PF-07242813 t_{1/2} predicted in human (17 days). Based on emerging data, the last out-patient visit schedule may be modified in the following cohorts to cover at least 4 half-lives of PF-07242813 observed in previous cohorts.

4.2.2. Study Design Rationale for Part 2

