4.3. Justification for Dose

4.3.1. Prediction of Human PK and Efficacious dose

Based on the serum PK parameter values observed for PF-07242813 in nonclinical species, the predicted 2-compartment PK parameter values in humans are expected to be the same as those of a typical therapeutic IgG mAb. These values have been reported previously (Dirks and Meibohm 2010; Betts et al. 2018)^{8,2} and were used for the PF-07242813 human PK predictions as follows: 3.2 L for central volume, 2.2 L for peripheral volume, 0.25 L/day for central CL, 0.45 L/day for distributive clearance, 0.26 1/day for SC absorption rate constant and 60% for SC bioavailability. The predicted volume and clearance values resulted in a 17-day $t_{1/2}$ and a 5.4 L V_{ss} .

As there are no validated mechanism-based biomarkers or preclinical disease/efficacy model for human AD, the efficacious dose of PF-07242813 has been projected empirically, as a dose that will achieve >95% CD1a receptor occupancy at steady state trough concentrations at the site of action (skin). A site of action model was used to link PF-07242813 exposure to CD1a receptor occupancy using the PF-07242813 K_D and the predicted human PK parameters, CD1a concentrations in skin and CD1a internalization/turnover rate. Using this approach, the predicted efficacious human dose of PF-07242813 is estimated to be 30 mg SC q4wk. The projected steady state AUC_{tau} ($\tau=4$ weeks/672 hrs), C_{ave} and C_{max} associated with the predicted efficacious dose are 1730 $\mu\text{g.h/mL}$, 2.58 $\mu\text{g/mL}$ and 3.67 $\mu\text{g/mL}$.

4.3.2. Dose Rationale for Part 1

The nonclinical safety profile of PF-07242813 has been adequately characterized to support development into human clinical studies of up to 3 months in duration. No test article-related effects or target organs were identified following once weekly administration of PF-07242813 in a pivotal 13-week cynomolgus monkey toxicity study with the NOAEL defined as the highest dose tested, 200 mg/kg/week (IV). In this study, the C_{max} and AUC_{168H} exposure limit for dose escalation are set to be 1020 μ g/mL and 106000 μ g/mL, respectively, determined as 1/10th of the mean exposures observed at NOAEL in the monkey toxicity study.

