A single dose of study intervention is planned in 24 adult participants with AD (Cohort 9), at the maximum tolerated dose (MTD) observed in Part 1 or the highest dose studied in Part 1 if MTD is not achieved (eg, the planned maximum dose of 1000 mg). Following a 1000 mg single IV dose of PF-07242813, the predicted CD1a receptor occupancy would be saturated and remain high (>95%) for greater than 16 weeks. An optional cohort (Cohort 16) may be used to evaluate further IV or SC dosing of PF-07242813, based on cumulative safety and PK data from Part 1 and Cohort 9 in Part 2.

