7. DISCONTINUATION OF STUDY INTERVENTION AND OF STUDY PARTICIPANT DISCONTINUATION/WITHDRAWAL

7.1. Discontinuation of Study Intervention

Note that discontinuation of study intervention does not represent withdrawal from the study. If study intervention is definitively discontinued, the participant will remain in the study to be evaluated for a minimum of 4 half-lives (approximately 70 days) after last dose. See the [SoA](#) for data to be collected at the time of discontinuation of study intervention and follow-up for any further evaluations that need to be completed.

In rare instances, it may be necessary for a participant to permanently discontinue study intervention (definitive discontinuation). Reasons for definitive discontinuation of study intervention include the following:

- Any participant who develops Grade 2 or higher adverse events for cardiac and blood/bone marrow categories and Grade 3 or higher adverse events in all other categories according to criteria defined in CTCAE, v. 5 will be discontinued from treatment, and followed until resolution of the adverse event(s).
- If a participant experiences symptoms typical of an allergic reaction, the study drug administration should be discontinued immediately and permanently;
- ECG changes (see below);
- Unacceptable toxicity;
- Pregnancy.

ECG Changes

A participant who meets the bulleted criteria based on the average of triplicate ECG readings will be withdrawn from the study intervention.

- QTcF >500 msec.

- Change from baseline: QTc >60 msec.

If a clinically significant finding is identified (including, but not limited to, changes from baseline in QTcF after enrollment), the investigator or qualified designee will determine if the participant can continue in the study and if any change in participant management is needed. This review of the ECG printed at the time of collection must be documented. Any new clinically relevant finding should be reported as an AE.

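### Section 10.4.2 equates the 60-day contraception period with seven terminal half-lives, but at the protocol's 17-day half-life seven is 119 days and 60 days is about 3.5

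*Protocol*

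**What the plan says.** Section 10.4.2 has one bullet for Part 1 and one for Part 2. Each requires contraception "as described below during the intervention period and for at least 60 days", and the label follows directly: "for at least 60 days ($7 \times$ terminal half-life) after the last dose of study intervention". Each adds that this is a period "which corresponds to the time needed to eliminate any reproductive safety risk of the study intervention(s").

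Elsewhere the protocol works with a longer half-life:

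- Section 4.3.1: "The predicted volume and clearance values resulted in a 17-day" half-life.
- Section 4.2.1 uses the same 17 days to set the last outpatient visit at about 70 days after dosing, described as more than four half-lives.
- Section 7.1 keeps participants who stop study intervention in the study to be "evaluated for a minimum of 4 half-lives (approximately 70 days) after last dose".
- Section 8.3.5.1 collects pregnancy details until 28 days or five terminal half-lives after the last dose, whichever is longer.
- Section 4.3.3, for a single 1000 mg IV dose: "the predicted CD1a receptor occupancy would be saturated and remain high (>95%) for greater than 16 weeks".

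**The concern.** A period cannot be both 60 days and seven half-lives unless the half-life is about 8.6 days, and no section gives such a value. The same protocol says that four half-lives take longer than this supposed seven.

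This is an operative safety criterion. Section 4.2 says that human reproductive safety data are not available and requires highly effective contraception for that reason. A participant who stops contraception on day 61 complies with the protocol and has been told that the risk is over. On the protocol's own predictions, at the top doses she would still carry drug at concentrations above those projected for efficacy.

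**Working it through.** **Inputs**

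- Contraception period of 60 days, labelled 7 half-lives (Section 10.4.2).
- Predicted terminal half-life of 17 days (Sections 4.2.1 and 4.3.1).
- Four half-lives taken as about 70 days (Section 7.1).
- Two-compartment parameters (Section 4.3.1): "3.2 L for central volume, 2.2 L for peripheral volume, 0.25 L/day for central CL, 0.45 L/day for distributive clearance".
- Projected steady-state Cmax at the predicted efficacious dose of 30 mg SC every 4 weeks: 3.67 µg/mL (Section 4.3.1).

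**1. Reproduce the protocol's half-life.** The rate constants are:

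- k10 = 0.25/3.2 = 0.0781 per day
- k12 = 0.45/3.2 = 0.1406 per day
- k21 = 0.45/2.2 = 0.2045 per day

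Their sum is 0.4233, and k10 × k21 = 0.01598. The slow rate is β = [0.4233 − √(0.4233² − 4 × 0.01598)]/2 = 0.0419 per day, and the fast rate is α = 0.3814 per day. The terminal half-life is ln 2/0.0419 = 16.5 days, close to the stated 17.

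**2. Try to reproduce 60 days as seven half-lives.**

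| Half-life used (days) | 7 half-lives (days) | Half-lives in 60 days | Fraction left at 60 days |
|---|---|---|---|
| 16.5 (re-derived) | 116 | 3.6 | 8.1% |
| 17 (stated) | 119 | 3.5 | 8.7% |
| 17.5 (70/4) | 122.5 | 3.4 | 9.3% |

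The fraction left is 2^(−60/half-life). After seven half-lives it would be 2^(−7) = 0.8%. None of the three values gives 60 days. Working backwards, 60/7 = 8.6 days, about half the protocol's figure. The shortfall at 17 days is 119 − 60 = 59 days.

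**3. What remains at day 60.** By then the fast phase is negligible. For a single 1000 mg IV dose, treated as a bolus,

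C(60) = (1000/3.2) × [(0.2045 − 0.0419)/(0.3814 − 0.0419)] × exp(−0.0419 × 60) = 312.5 × 0.479 × 0.081 ≈ 12.1 µg/mL.

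That is about 3.3 times the 3.67 µg/mL comparator (12.1/3.67). At day 119 the same model gives about 1.0 µg/mL.

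**4. Other planned doses.** The same linear model, with the SC absorption rate of 0.26 per day and 60% bioavailability from Section 4.3.1, gives these levels 60 days after the last dose:

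| Regimen | Level at 60 days (µg/mL) | Above 3.67? |
|---|---|---|
| 100 mg IV, single | 1.2 | No |
| 300 mg IV, single | 3.6 | No, marginally |
| 1000 mg IV, single | 12.1 | Yes |
| 150 mg SC × 3 | 2.4 | No |
| 300 mg SC × 3 | 4.9 | Yes |
| 1000 mg IV × 3 (maximum for optional Cohort 14) | 22.6 | Yes |

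**5. Compare with the protocol's other windows.** Five half-lives for pregnancy details are 5 × 17 = 85 days, so between days 60 and 85 the protocol still collects pregnancy details but no longer requires contraception. The last Part 2 contraception check in Table 3 is on Day 113, which is 112 days after dosing, or 112/17 = 6.6 half-lives.

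**The case against.** The strongest reply accepts the arithmetic and disputes the consequence.

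- **Part 2 checks.** Table 3 has a contraception check at every visit to Day 113, and Section 5.3.4 has the investigator restate the need for contraception at those time points. Most Part 2 women would therefore be told to continue to about 6.6 half-lives. This is a real mitigation. It also gives sites two different end dates, and Section 10.4.2 remains the requirement.
- **Part 1 methods.** Permitted methods are non-hormonal and of low user dependency, so they are seldom stopped on a given day. Pregnancy tests run to Day 71 (single dose) or Day 99 (multiple dose), although Cohorts 1 to 3 may finish earlier. This stands, but Tables 1 and 2 show no contraception check, so the gap is least covered here.
- **No suspected teratogenicity.** Sections 4.2 and 4.2.2 say so, and nothing in the documents makes serum level or receptor occupancy a threshold for reproductive risk. This could justify a shorter period. It does not justify calling that period seven half-lives.
- **Receptor occupancy.** Section 4.3.3 predicts high occupancy for more than 16 weeks without giving an end, so 119 days might also end during it. That is right: occupancy shows that 60 days ends early, but it does not select 119.
- **Top-dose exposure.** Most planned regimens fall below 3.67 µg/mL by day 60. That is also right, although 1000 mg is the planned maximum for Cohort 9.
- **Predicted half-life.** Seventeen days is a prediction, and monkeys showed non-linear kinetics. But the protocol plans on it throughout, and Section 10.4.2 has no provision for adjusting the period to observed data.

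**Conclusion.** The point holds. Sixty days is not seven terminal half-lives on any half-life in the documents. It is about 3.5 (3.4 to 3.6), and seven would be 119 days (116 to 122.5), so the stated period is about half of what its label claims. The contradiction itself needs no model, since Section 7.1 makes four half-lives longer than 60 days.

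The exposure figures rest on the protocol's predicted, linear two-compartment kinetics. They show that the risk-elimination statement is unsupported at the highest doses, not that harm is expected. The documents do not reveal whether the days or the multiple is the mistake. No endpoint, analysis or sample size is affected. Because this is a wrong figure in a participant-safety criterion, it must be corrected.

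**What to change.** Amend both bullets of Section 10.4.2 so that the duration, the multiple and the half-life agree with each other and with Sections 4.2.1, 4.3.1 and 7.1. There are two consistent forms:

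1. If seven half-lives is intended, state about 119 days.
2. If 60 days is intended, describe it as about 3.5 half-lives, give the reason it is sufficient, and remove the statement that it covers elimination of any reproductive risk.

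The clinical team chooses. The text should also say whether the period will be revised if the observed half-life differs from 17 days, as Section 4.2.1 already does for follow-up visits.

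The contraception and pregnancy checks should then be aligned with the chosen date. In Part 2 they already run to Day 113. In Part 1 an instruction at the last visit would do, and longer follow-up is not needed for this correction. The cost is amendment wording in two bullets and the matching consent text.
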